Exploratory Objectives:	
• Investigate repeatability of whole-body ⁶⁸Ga-PSMA-generator Ki Patlak imaging against that of conventional whole-body ⁶⁸Ga-PSMA- SUV imaging in patients with confirmed metastatic prostate adenocarcinoma.

- Evaluate equivalence of whole-body ⁶⁸Ga-PSMA Ki Patlak imaging between the two processes to create ⁶⁸Ga-HBED-PSMA (⁶⁸GA-PSMA-cyclotron vs. ⁶⁸Ga-PSMA-generator)

Endpoints:

The primary endpoint of this study is to prove equivalence between the cyclotron and generator produced radioisotope. To meet this endpoint we will make a direct comparison of the ⁶⁸GA-PSMA-cyclotron vs. ⁶⁸Ga-PSMA-generator scans obtained within 24-48h. We will measure SUVmean and SUVmax of the same Regions of Interest (ROI) in both scans using the PET analysis software we use in our clinical practice. The two scans will be retrieved and the exact same ROIs will be drawn at the same time for the two scans (software offers a copy-paste function so that no discrepancies exist between the two measurements). The SUVmean and SUVmax obtained from both scans for each Region of Interest will then be analyzed to determine the within-subject coefficient of variation value as measured by the Bland Altman analysis.

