3.1 Overall Design

Thirty patients with metastatic prostate cancer that have undergone standard-of-care staging at WCMC will be considered for enrollment. For this study, enrolled patients will undergo a total of two whole-body dynamic ^{68}Ga -PET scan protocols of at least 0-75 min and at most 0-90 min scan time post injection, depending on the amount of injected dosage. A 6 to 48 hour gap will be introduced between the two scans. The first scan will occur after a baseline clinical evaluation, which will include a history, physical, and baseline lab draw. Blood work will be obtained before, during and after the scan. The radiotracers will be evaluated for repeatability and equivalence across the different production methods. This will include basic pharmacokinetics, distribution, metabolism and excretion.

Up to 30 patients will undergo each two whole-body dynamic scans, initially with ^{68}Ga -PSMAcyc and later with ^{68}Ga -PSMagen (with a minimum time of 6 h and maximum time of 2 days between the two injections). All patients will receive ^{68}Ga -PSMagen from the CBIC core and ^{68}Ga -PSMAcyc from NCM pharmaceuticals at a specific activity of 1-2 Ci/ μmol , the typical specific activity used in published clinical trials with ^{68}Ga -PSMA (10).

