11.2.5 Record Retention

Essential documents are those documents that individually and collectively permit evaluation of the study and quality of the data produced. After completion of the study, all documents and data relating to the study will be kept in an orderly manner by the Investigator in a secure study file. Essential documents should be retained for 2 years after the final marketing approval in an ICH region or for at least 2 years since the discontinuation of clinical development of the IP. In addition, all subjects medical records and other source documentation will be kept for the maximum time permitted by the hospital, institution, or medical practice.

12. Statistical Considerations

Up to 30 patients will undergo a dynamic whole-body scan with ^{68}Ga -PSMA_{Gen} and later ^{68}Ga -PSMA_{cyc} with a maximum time of 2 days and a minimum time of 6 h between the two injections. All 22 patients will receive ^{68}Ga -PSMA_{Gen} at a specific activity of 1-2 Ci/ μmol , the typical specific activity used in clinical trials with ^{68}Ga -PSMA. We expect the ^{68}Ga -PSMA_{cyc} to be delivered and injected at a specific activity of 0.1- 2.0 Ci/ μmol given the rigors of delivery. We will accept doses in this range as the prior small animal imaging was designed to understand the affect of specific activity over a 20X range.

For a power of 80% a calculation of the sample size needed to test odds ratio (equality test) was performed. A sample size of 22 would give a power percentage of 18.47 with a type 1 error of 5%. This power percentage is sufficient in providing confidence that the findings will reflect a true effect. The median statistical power of studies in the neurosciences is between ~8% and ~31%. We will not and should not be focusing on p-values but rather the estimates of the effect size with its confidence intervals.

Estimating repeatabilities using a mixed effects model framework has proven to be powerful, the repeatability (r) is calculated as the variance among group means (group-level variance) over the sum of group-level and data-level (residual) variance (v). A Pearson's correlation coefficient will demonstrate also present the repeatability of results. Intraclass correlation values for both groups will be calculated to test if the groups differ in repeatability. These collection of tests(functions) for estimating repeatability of measurements with a single grouping factor are all performed in R statistical software.

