To quantify the agreement between the two scans, we will use the repeated measures correlation coefficient to account for multiple observations per subject. We will calculate the repeated measures correlation-coefficient for the SUVmax and SUVmean for reference regions as well as regions suspicious for metastatic disease. We will measure SUVmean and SUVmax of the same Regions of Interest (ROI) in both scans using the PET analysis software we use in our clinical practice. The two scans will be retrieved and the exact same ROIs will be drawn at the same time for the two scans (software offers a copy-paste function so that no discrepancies exist between the two measurements). The SUVmean and SUVmax obtained from both scans for each Region of Interest will then be analyzed to determine the within-subject coefficient of variation value as measured by the Bland Altman analysis. If the agreement between the two scans lies within an acceptable rate (which we consider 30% based on previously published data), we will consider the two methods equivalent.

Also, as aforementioned the Bland-Altman Test presents proof of repeatability analysis.

13. Adverse Event Reporting Requirements

Adverse event (AE) monitoring and reporting is a routine part of every clinical trial. The investigator will be required to provide appropriate information concerning any findings that suggest significant hazards, contraindications, side effects, or precautions pertinent to the safe use of the drug or device under investigation. Safety will be monitored by evaluation of adverse events reported by subjects or observed by investigators or research staff, as well as by other investigations such as clinical laboratory tests, x-rays, electrocardiographs, etc.

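### The 30% rule that decides the primary equivalence endpoint has no formula, no scale, no limit on the mean cyclotron/generator SUV ratio and no confidence bound, so the verdict depends on the formula chosen

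*Combined protocol and SAP*

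**What the plan says.** The synopsis (section 1, Endpoints) sets the aim: "The primary endpoint of this study is to prove equivalence between the cyclotron and generator produced radioisotope". It says that SUVmean and SUVmax from identical ROIs on both scans will be "analyzed to determine the within-subject coefficient of variation value as measured by the Bland Altman analysis". It gives no threshold.

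Section 12 repeats that description and adds the only decision rule in the document: when agreement of the paired scans "lies within an acceptable rate (which we consider 30% based on previously published data), we will consider the two methods equivalent". No citation is attached to the 30%.

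Two other statements in section 12 bear on the rule:
- Agreement is also linked to another statistic: "To quantify the agreement between the two scans, we will use the repeated measures correlation coefficient to account for multiple observations per subject". It is to be calculated "for the SUVmax and SUVmean for reference regions as well as regions suspicious for metastatic disease". No threshold is given for it.
- Emphasis is to be placed not on p-values "but rather the estimates of the effect size with its confidence intervals". This is a general preference, and no interval is attached to the 30%.

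Nowhere does the plan say whether SUV differences are taken raw, as percentages or on the log scale, or whether the mean difference between products enters the CV. It also does not say which SUV measure or which type of ROI decides.

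**The concern.** A within-subject CV describes scatter between paired scans. Equivalence of two products is a statement about the systematic ratio between them. A CV limit controls that ratio only if the formula lets the mean difference in, and the plan does not say whether it does. A Bland-Altman report would normally show the mean bias, but the rule does not act on it. The rule also uses a point estimate, so it takes no account of uncertainty from 22 or 30 patients.

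A systematic SUV shift is what the study has to exclude. Section 2.3 presents proof of equivalence as a way to relieve the cost and supply limits of generator production. Section 12 accepts cyclotron product at 0.1-2.0 Ci/µmol against 1-2 Ci/µmol for generator product. If the formula is settled after the data are seen, that choice can reverse the primary conclusion.

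**Working it through.** **The plan's own figure.** The plan reports no operating characteristics for the 30% rule. Its one power figure (18.47% with 22 patients) is for an odds-ratio test. No odds ratio or event rates are given, so it cannot be reproduced, and nothing below uses it.

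**Inputs.** From the plan: the 30% limit, and 22 or up to 30 patients (section 12). Assumed, not in the documents: log-normal SUVs, one scan pair per patient, test-retest CV 10/15/20/25%, and, for the raw scale only, between-patient CV 30/60/100%. Write *r* for the true cyclotron/generator ratio.

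**Reading A: CV from the SD of percent or log differences (bias excluded).** On the log scale *r* cancels. The pass probability is P(χ² on n−1 df ≤ (n−1)·ln(1.09)/ln(1+CV²)).
- CV 25%, n=22: 21 × 0.0862/0.0606 = 29.9, giving 90.5%. With n=30: 93.4%.
- CV 20%: 99.9% (n=22) and 99.98% (n=30). At CV 10-15%: about 100%.
- On the percent scale, simulation at *r* = 2 gives at least 99.3% throughout.

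**Reading B: CV from the SD of raw SUV differences over the grand mean (bias excluded).** A proportional shift now enters through the spread between patients. Without noise, the CV at *r* = 2 is (1/1.5)/√2 = 0.471 times the between-patient CV. That is 14%, 28% and 47% for between-patient CV 30%, 60% and 100%. Simulated pass rates at *r* = 2, for test-retest CV 10/15/20/25%:

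| Between-patient CV | n=22 | n=30 |
|---|---|---|
| 30% | 100/97/83/53% | 100/98/85/52% |
| 60% | 61/47/30/17% | 59/42/25/12% |
| 100% | 9/8/6/4% | 5/4/3/2% |

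**Reading C: CV with bias retained (root mean square of the differences).** At *r* = 2 the shift alone gives (1/1.5)/√2 = 47% on the percent scale, or √(exp((ln 2)²/2) − 1) = 52% on the log scale, so it passes 0%. The noise-free break-even ratio solves |r−1|/((1+r)/2)/√2 = 0.30, giving 1.54 (percent), or equals exp(√(2·ln 1.09)) = 1.51 (log). The 30% thus acts as an unstated ratio margin of about 1.5. At n=22, *r* = 1.4 passes 99/84/53/27% (percent) or 96/69/36/16% (log).

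**Reading D: 30% applied to the mean percent difference.** *r* = 2 passes 0%. At n=22, *r* = 1.4 passes 14/25/32/36%.

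**Reading E: limits of agreement within ±30%.** This needs a test-retest CV below 0.30/(1.96·√2) = 10.8% even with no bias. *r* = 2 passes 0%. At n=22, identical products pass about 55% at CV 10%, about 1% at 15% and 0% at 20% or more.

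**Correlation.** Multiplying every cyclotron SUV by a constant leaves a correlation coefficient unchanged, so it carries no information on *r*.

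**The case against.** The strongest reply is that a reader might infer from Reading A that a twofold SUV difference would be declared equivalent under this plan. The documents do not support that. They fix no scale and do not say that bias is excluded. On raw differences a twofold ratio can fail most of the time, and under Readings C, D and E it always fails. What can be supported is that the verdict depends on an unstated formula.

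Two other strong readings also fail. A reader might infer that the correlation is the equivalence criterion, because section 12 links it to agreement. It has no threshold, and the CV named just before the rule is the natural referent of 30%. A reader might infer that 30% is too wide. The published data behind it are neither cited nor available here, so its adequacy cannot be judged.

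On several ROIs per patient, section 12 is not silent. It describes analysis of each ROI, names a correlation that allows for repeated observations and plans mixed-model repeatability. None of these is linked to the 30% decision, so ROI handling is a secondary gap.

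Finally, every pass rate rests on CVs that are not in the plan and on one pair per patient. That limits the exact percentages. It does not touch the absence of a formula, a ratio limit and a confidence bound.

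**Conclusion.** The point stands, and it bears on the primary conclusion. The 30% rule is the only route to declaring equivalence and cannot establish it as written. For a true twofold ratio, the pass rate is 90% or more from percent or log differences, about 100% down to 2-4% from raw differences, and 0% under the other three readings. With bias retained, 30% works as a ratio margin near 1.5 that the plan never states. Read as limits of agreement, the rule rejects identical products about 45% of the time at CV 10% and nearly always at 15%.

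These figures assume log-normal SUVs, one pair per patient, 22 or 30 patients, test-retest CV 10-25% and, for raw differences, between-patient CV 30-100%. A confidence bound on the CV alone would not cure the problem, because a log-scale CV without bias ignores the ratio at any precision. The ratio itself needs a limit.

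**What to change.** In section 12 and the synopsis, replace the rule as follows.

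- Declare equivalence only if the 90% CI of the cyclotron/generator geometric mean SUV ratio lies wholly within a ratio margin that is stated and justified in advance. An example is 1/1.30 to 1.30, which is an assumed translation of the plan's 30%.
- Estimate the ratio from per-ROI log ratios with a patient effect, to allow for several ROIs per patient.
- State in advance which SUV measure and which ROI type decide.
- Report within-subject CV, bias and limits of agreement with CIs as description. Do not use a correlation as evidence of equivalence.

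**Cost.** Text changes, a restated sample-size rationale and a stricter criterion, with no new data. At the example margin with one pair per patient, identical products pass 100/100/99/92% (n=22) and at least 98% (n=30) at assumed CV 10/15/20/25%. A true ratio of 1.30 passes about 5%, and 1.4 passes at most about 0.4%. Requiring several criteria to pass together would lower power.

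Sections 3.1 and 12 give opposite scan orders. That is a separate matter and the sections must be reconciled. If all patients have the same order, product remains confounded with order and this test cannot remove that.

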13.1 Adverse Event Definition

An adverse event (also referred to as an adverse experience) can be any unfavorable and unintended sign (e.g., an abnormal laboratory finding), symptom, or disease temporally associated with the use of a drug, and does not imply any judgment about causality. An adverse event can arise with any use of the drug (e.g., off-label use, use in combination with another drug) and with any route of administration, formulation, or dose, including an overdose.

13.1.1 Investigational Agent or Device Risks (Expected Adverse Events)

The non-radiation exposure related risks that may be experienced during the scans are related to the radiotracer infusion and can be:

- Bruising or bleeding at the site of the radiotracer injection
- Infection at the site of injection
- Allergic type reaction

13.1.2 Adverse Event Characteristics and Related Attributions

CTCAE term (AE description) and grade: The descriptions and grading scales found in the revised NCI Common Terminology Criteria for Adverse Events (CTCAE) version 5.0 will be utilized for AE reporting. A copy of the CTCAE version 5.0 can be downloaded from the CTEP web site (<http://ctep.cancer.gov>).

- **Attribution** of the AE:
 - Definite – The AE is *clearly related* to the study treatment.
 - Probable – The AE is *likely related* to the study treatment.
 - Possible – The AE *may be related* to the study treatment.
 - Unlikely – The AE is *doubtfully related* to the study treatment.
 - Unrelated – The AE is *clearly NOT related* to the study treatment.
 -

13.1.3 Recording of Adverse Events

All adverse events will be recorded on a subject specific AE log. The AE log will be maintained by the research staff and kept in the subject's research chart.

13.1.4 Reporting of AE to WCM IRB

All AEs occurring on this study will be reported to the IRB according to the IRB policy, which can be accessed via the following link:
[http://researchintegrity.weill.cornell.edu/forms_and_policies/forms/Immediate_Reportin...pdf](http://researchintegrity.weill.cornell.edu/forms_and_policies/forms/Immediate_Reportin...)

13.2 Definition of SAE

SAEs include death, life threatening adverse experiences, hospitalization or prolongation of hospitalization, disability or incapacitation, overdose, congenital anomalies and any other serious events that may jeopardize the subject or require medical or surgical intervention to prevent one of the outcomes listed in this definition. (*Modify as necessary*)

13.2.1 Reporting of SAE to IRB

All SAEs occurring on this study will be reported to the IRB according to the IRB policy, which can be accessed via the following link:

http://researchintegrity.weill.cornell.edu/forms_and_policies/forms/Immediate_Report_Policy.pdf.

13.2.2 Reporting of SAE to FDA

IND application sponsor must report any suspected adverse reaction or adverse reaction to study intervention that is both serious and unexpected. Unexpected fatal or life-threatening suspected adverse reactions represent especially important safety information and must be reported to FDA as soon as possible but no later than 7 calendar days following the sponsor's initial receipt of the information.

- i. death,
- ii. a life-threatening adverse event,
- iii. in-patient hospitalization or prolongation of existing hospitalization,
- iv. a persistent or significant incapacity or substantial disruption of the ability to conduct normal life functions, or
- v. a congenital anomaly or birth defect

Important medical events that may not result in death, be life-threatening, or require hospitalization may be considered serious when, based upon appropriate medical judgment, they may jeopardize the patient or research subject and may require medical or surgical intervention to prevent one of the outcomes listed as serious

CDER INDs:

Food and Drug Administration
Center for Drug Evaluation and Research
Division of Investigational Products
[name]
[name]

13.3 AE/SAE Follow Up

All SAEs and AEs reported during this study will be followed until resolution or until the investigator confirms that the AE/SAE has stabilized and no more follow-up is required. This requirement indicates that follow-up may be required for some events after the subject discontinues participation from the study.

13.4 Time Period and Frequency for Event Assessment and Follow Up

The occurrence of an adverse event (AE) or serious adverse event (SAE) may come to the attention of study personnel during study visits and interviews of a study participant presenting for medical care, or upon review by a study monitor.

All AEs including local and systemic reactions not meeting the criteria for SAEs will be captured on the appropriate case report form (CRF). Information to be collected includes event description, time of onset, clinician's assessment of severity, relationship to study product (assessed only by those with the training and authority to make a diagnosis), and time of resolution/stabilization of the event. All AEs occurring while on study must be documented appropriately regardless of relationship. All AEs will be followed to adequate resolution.

Any medical condition that is present at the time that the participant is screened will be considered as baseline and not reported as an AE. However, if the study participant's condition deteriorates at any time during the study, it will be recorded as an AE.

Changes in the severity of an AE will be documented to allow an assessment of the duration of the event at each level of severity to be performed. AEs characterized as intermittent require documentation of onset and duration of each episode.

All reportable events will be recorded with start dates occurring any time after informed consent is obtained until 7 (for non-serious AEs) or 30 days (for SAEs) after the last day of study participation. At each study visit, the investigator will inquire about the occurrence of AE/SAEs since the last visit. Events will be followed for outcome information until resolution or stabilization.

14. Unanticipated Problems Involving Risks to Subjects or Others

14.1 Definition of Unanticipated Problems Involving Risks to Subjects or Others (UPIRTSO)

The reporting of UPIRTSOs applies to non-exempt human subjects research conducted or supported by HHS. Provide the definition of an UPIRTSO being used for this clinical trial. An incident, experience, or outcome that meets the definition of an UPIRTSO generally will warrant consideration of changes to the protocol or consent in order to protect the safety, welfare, or rights of participants or others. Other UPIRTSOs may warrant corrective actions at a specific study site. Examples of corrective actions or changes that might need to be considered in response to an UPIRTSO include:

- Modification of inclusion or exclusion criteria to mitigate the newly identified risks
- Implementation of additional safety monitoring procedures
- Suspension of enrollment of new participants or halting of study procedures for enrolled participants
- Modification of informed consent documents to include a description of newly recognized risks
- Provision of additional information about newly recognized risks to previously enrolled participants.

14.1.2 Unanticipated Problem Reporting

The investigator will report unanticipated problems (UPIRTSOs) to the reviewing Institutional Review Board (IRB) and to the Data Coordinating Center (DCC)/lead principal investigator (PI). The UPIRTSO report will include the following information:

- Protocol identifying information: protocol title and number, PI's name, and the IRB project number;
- A detailed description of the event, incident, experience, or outcome;
- An explanation of the basis for determining that the event, incident, experience, or outcome represents an UPIRTSO;
- A description of any changes to the protocol or other corrective actions that have been taken or are proposed in response to the UPIRTSO.

To satisfy the requirement for prompt reporting, UPIRTSOs will be reported using the following timeline:

- UPIRTSOs that are serious adverse events (SAEs) will be reported to the IRB and to the DCC/study sponsor within <insert timeline in accordance with policy> of the investigator becoming aware of the event.
- Any other UPIRTSO will be reported to the IRB and to the DCC/study sponsor within <insert timeline in accordance with policy> of the investigator becoming aware of the problem.
- All UPs should be reported to appropriate institutional officials (as required by an institution's written reporting procedures), the supporting agency head (or designee), Food and Drug Administration (FDA), and the Office for Human Research Protections (OHRP) within <insert timeline in accordance with policy> of the IRB's receipt of the report of the problem from the investigator.]

References

